# 12.7.4 Secondary multi-variable Cox models

We fill additionally fit a series of exploratory, bivariate Cox models. These models will be fit as above but will include only two markers. The sets of two markers that we consider are

- 1. binding Ab to RBD and pseudovirus neutralization ID50
- 2. binding Ab to RBD and live virus neutralization MN50

As above, Wald tests will be used to evaluate the null hypothesis of no association between any marker and hazard of COVID-19. Hazard ratios will be reported per standard deviation increase alongside 95% confidence intervals.

# 13 Correlates of Protection: Generalities

In general, for all of the correlate of protection analyses, the same antibody markers are assessed that were analysed as correlates of risk: the Day 57 antibody markers not subtracting for the Day 1 baseline readout are used. Each of the five Day 57 antibody biomarkers are separately studied as CoPs by the different analysis approaches summarized below.

#### 13.0.1 [With Day 29 markers]

If Day 29 markers are included, then the same CoP analyses are done as for each of the five Day 57 markers, where, as for the CoR analyses, now the time origin is the Day 29 visit date and endpoint cases are counted starting 7 days after the Day 29 visit date.

# 14 Correlates of Protection: Correlates of Vaccine Efficacy Analysis Plan

For each of the five Day 57 antibody biomarkers, the method of Gilbert, Blette, Shepherd, and Hudgens (2020) will be used to estimate VE(1), VE(0), and VE(1) - VE(0), each with a 95% confidence interval and a 95% estimated uncertainty interval (EUI), where VE(1) is vaccine efficacy for the subgroup of vaccine recipients with Day 57 marker if assigned vaccine S(1)above a specified cut-point value  $s_{cut}$ , and VE(0) is vaccine efficacy for the subgroup of vaccine recipients with Day 57 marker if assigned vaccine S(1)not greater than  $s_{cut}$ . That is,

$$VE(1) = 1 - \frac{P(Y(1) = 1 | S(1) > s_{cut})}{P(Y(0) = 1 | S(1) > s_{cut})}$$
$$VE(0) = 1 - \frac{P(Y(1) = 1 | S(1) \le s_{cut})}{P(Y(0) = 1 | S(1) \le s_{cut})}$$

The analysis will be done under the **NEH** assumption ("no early harm") of Gilbert et al. (2020). The cut point is defined as the percentile equal to one minus the estimated vaccine efficacy in the primary analysis, with logic that a maximally simple version of a perfect CoP would have binary marker with S = 1 corresponding to protection and S = 0 corresponding to no protection. If the estimated vaccine efficacy is high (say 90% or higher), it is possible that this cutpoint will not yield stable results, because of sparse cells; in this situation we will repeat the analysis using two additional cut-points that creates greater balance in frequencies of S = 1 and S = 0 in the vaccine group immunogenicity subcohort: 20th and 40th percentiles. If the estimated vaccine efficacy is moderate (between 50% and 80%), we will also use the two

additional cut-points the 20th and 40th percentiles. This analysis method does not require closeout placebo vaccination (CPV) (Follmann, 2006) or a good baseline immunogenicity predictor of the Day 57 antibody marker. The method is implemented using Bryan Blette's R package "psbinary" posted at his Github repository.

A limitation of the Gilbert et al. method is that it only assesses a binary biomarker. Other analyses will be considered to estimate VE(s) over biomarker values s over the entire range, treating S as a quantitative or categorical variable, and gaining efficiency by incorporating CPV and/or putative baseline immunogenicity predictors (BIPs). Based on earlier simulation studies (Follmann, 2006; Huang et al., 2013, e.g.,), methods that only leverage CPV data tend to have low power relative to methods that leverage BIP data alone (BIP-only methods) or both BIP and CPV data (BIP+CPV methods). Therefore, the key for improving efficiency will be the availability of a BIP. VE curve analysis for continuous S will thus be conducted contingent on the availability of a BIP that satisfies the  $R^2$  criterion outlined in Table 10. It is anticipated that post-crossover immune response marker data will not be available in early correlates analyses, and so BIP-only methods will be used in these initial analyses. When CPV data becomes available, new BIP+CPV analyses will be conducted that incorporate this new information. Details of the BIPs used can be found at the end of this section.

Let Y(a) denote the potential binary outcome of interest if receiving intervention a, with a = 1,0 standing for assignment to vaccine and placebo, respectively. Let S(a) denote the potential biomarker value if receiving intervention a. The vaccine efficacy curve (Follmann, 2006; Gilbert and Hudgens, 2008) is defined as the curve of vaccine efficacy as a function of the immune response biomarker if assigned vaccination (i.e., S(1)): VE(s) = 1 - P(Y(1) =1|S(1) = s)/P(Y(0) = 1|S(1) = s). It characterizes the percentage reduction in clinical risk under vaccine assignment compared to under placebo assignment conditional on S(1) and informs about the magnitude of potential immune response associated with certain levels of VE. Consider the existence of BIPs X correlated with S(1) and/or a CPV component in the trial where a subset of placebo recipients free of the outcome are vaccinated and have

their immune response biomarkers measured as substitutes for S(1). Under the NEE assumption and assuming the set of participants with S(1) available is nested within the set of participants with BIP measures, the pseudo-score estimation method (Huang et al., 2013; Zhuang et al., 2019) based on discrete BIP measures allowing for adjustment of X will be adopted for estimating the risk model P(Y(z) = 1 | S(1), X) and subsequently  $VE(s) = 1 - \int P(Y(1) = 1) P(Y(1)) P(Y(1))$  $1|S(1), x)dF_X(x|S(1)) / \int P(Y(0) = 1|S(1), x)dF_X(x|S(1)))$ . Hypothesis testing will be conducted for testing the null hypothesis that the VE curve is constant (Zhuang et al., 2019). Estimated parametric (Gilbert and Hudgens, 2008), semiparametric (Huang and Gilbert, 2011), or nonparametric (Li and Luedtke, 2020) likelihood estimators of VE curves will be applied to continuous BIPs. In scenarios where some BIPs are not measured from all trial participants, VE curve estimators accounting for this monotone missingness in X and S(1) will be adopted (Huang, 2018). If the data support positive vaccine efficacy before Day 57, sensitivity analysis approaches will be conducted for VE curve estimation under the NEH assumption. In the presence of multiple candidate biomarkers and when a CPV component is present, a multiple imputation approach as proposed in Dasgupta and Huang (2019) will be utilized to impute missing S(1) data for selecting markers from multiple candidates and deriving a univariate marker score for VE curve estimation.

Finally, for scenarios with very rare events such that methods described above lack precision even with a CPV component but where the available BIP still satisfies the  $R^2$  criterion outlined in Table 10, we will adopt sensitivity analysis methods that model the placebo risk conditional on the counterfactual S(1) based on a sensitivity parameter that varies over some pre-specified range.

Among different strategies to identify BIPs, the following will be tried. First, for vector vaccines, we will study Day 1 bAb or nAb response to the vector as a BIP for the Day 57 markers of interest. Second, we will check whether Day 1 bAb or nAb to Nucleocapsid protein is a BIP for the anti-Spike/anti-RBD Day 57 markers of interest. The rationale for this latter analysis is that some studies have shown cross-reactive responses to Nucleocapsid protein and to common circulating human coronaviruses.

We will also evaluate using a multivariate BIP that corresponds to all of these aforementioned candidate univariate BIPs, which may help to achieve the target  $R^2$  (see Table 10). When doing this, a separate BIP W will be used for each vaccine-induced immune response marker S(1). Let Y(a) be the counterfactual outcome of interest — e.g., a COVID disease endpoint by a prespecified time — if randomization assignment had been set to A = a. The analyses conducted will provide unbiased estimates of the estimands of interest when  $Y(a) \perp W|S(1)$  for  $a \in \{0, 1\}$ . The BIP W will be a learned function of baseline covariates L — that is, W = f(L) for a function f that will be learned based on the available data. All available baseline covariates will be considered for inclusion in L, including age, BMI, and Day 1 bAb or nAb to Nucleocapsid protein. If available, measurements of prior immune response to the vaccine vector (e.g., Day 1 bAb or nAb response to Ad26 for an Ad26 vector-based vaccine) will always be included in L.

If the trial of interest has more than 100 events on the vaccine arm in the subgroup of interest, then f will be chosen to be an estimate of the following population-level optimization problem:

minimize 
$$E[\{S - f(L)\}^2 | A = 1]$$
  
subject to  $f(L) \perp Y | A = 1, S$ .

The rationale for choosing f to (approximately) solve this optimization problem is that the BIP should be maximally predictive of S, while also satisfying the needed conditional independence assumption  $Y(a) \perp W|S(1)$  when a = 1. Moreover, the needed conditional independence assumption  $Y(a) \perp W|S(1)$ for the case that a = 0 is most plausible when this assumption is also satisfied for the case that a = 1. Also, because W = f(L) for some function f,  $Y(0) \perp W|S(1)$  is always more plausible than  $Y(a) \perp L|S(1)$ .

The solution to the above optimization problem is given by:

$$f(\ell) := \theta(\ell) - \frac{E[\theta(L)r(L)]}{E[r(L)^2]}r(\ell)$$

where  $\theta(\ell) := E\{S|A = 1, L = \ell\}, r(\ell) := \frac{m(\ell)}{E[m(L)]} - \frac{1-m(\ell)}{1-E[m(L)]}$  and  $m(\ell) := E[Y|A = 1, L = \ell]$ . The following strategy is used to estimate this solution:

- 1. Obtain an estimate  $\hat{\theta}$  of the function  $\theta$  by running a Superlearner of S against L in the vaccine arm, where inverse probability of sampling weights are used to account for two-phase sampling of the marker.
- 2. Obtain an estimate  $\hat{m}$  of m by using Superlearner to regress Y against L in the vaccine arm.
- 3. Obtain an estimate  $\hat{r}$  via a plug-in estimator, where E[m(L)] is estimated by taking the empirical mean of  $\hat{m}(L)$ .
- 4. The final estimate  $\hat{f}$  of f is given by

$$\hat{f}(\ell) := \hat{\theta}(\ell) - \frac{\hat{E}[\hat{\theta}(L)\hat{r}(L)]}{\hat{E}[\hat{r}(L)^2]}\hat{r}(\ell),$$

where  $\hat{E}$  denotes an empirical expectation.

Each Superlearner will be run using the same library and settings described in Table 9. If the trial has fewer than 100 events on the vaccine arm, then the function f will be learned via Step 1 above only — that is, we will take  $\hat{f} = \hat{\theta}$ . All standard errors will be obtained via the bootstrap, with the above fitting of  $\hat{f}$  redone within each bootstrap sample.

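### Section 14: the formula for the learned baseline immunogenicity predictor only balances its mean between cases and non-cases; it does not enforce the stated independence from outcome given the marker

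*Combined protocol and SAP*

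**What the plan says.** Section 14 introduces a multivariate baseline immunogenicity predictor (BIP) W = f(L), learned from the baseline covariates. "The analyses conducted will provide unbiased estimates of the estimands of interest when" Y(a) is independent of W given S(1), for both arms. The function f is meant to satisfy this in the vaccine arm: "the BIP should be maximally predictive of S, while also satisfying the needed conditional independence assumption".

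The projection rule applies under this condition: "If the trial of interest has more than 100 events on the vaccine arm in the subgroup of interest". The SAP then poses the minimisation of E[{S − f(L)}² | A=1] subject to f(L) being independent of Y given A=1 and S. It continues: "The solution to the above optimization problem is given by" f = θ − {E[θr]/E[r²]} r, where
- θ(L) = E[S | A=1, L],
- m(L) = E[Y | A=1, L],
- r = m/E[m] − (1 − m)/(1 − E[m]).

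Step 2 obtains m "by using Superlearner to regress Y against L in the vaccine arm". With fewer events the projection is skipped: "If the trial has fewer than 100 events on the vaccine arm, then the function f will be learned via Step 1 above only", so f is the estimate of θ. Table 10 in Section 16 allows the quantitative VE(s) analysis only if the BIP has R² of at least 0.25.

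**The concern.** The stated constraint conditions on S. The formula contains S only through θ, and m, r and the projection coefficient are all computed without it. A useful BIP predicts S. If S is also a correlate of risk, such a BIP will normally be associated with Y before S is taken into account. That marginal association is expected of a valid predictor, yet it is what the formula removes.

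Two things are at stake. A valid predictor could lose its signal, so that the quantitative VE(s) analysis is not run. Or a predictor could pass the R² requirement while breaking the condition on which unbiased estimation of VE(s) rests. This is a master plan for several trials, so the formula would be reused.

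**Working it through.** **1. What the formula enforces.** Write p = E[m]. Then

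r = m/p − (1 − m)/(1 − p) = (m − p)/{p(1 − p)}.

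Because f is the least-squares residual of θ on r, E[f r] = 0. Substituting r,

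E[f r] = E[f m]/p − E[f(1 − m)]/(1 − p) = E[f | Y=1, A=1] − E[f | Y=0, A=1].

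So the formula solves the problem with the constraint of equal mean f in cases and non-cases, averaged over S. The stated constraint is independence at each value of S.

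**2. A case checkable by hand (assumed values).** L is binary with probability 1/2 and affects Y only through S. Take θ = 0 and 1, and m = 0.012 and 0.008. θ minimises the squared error and already meets the constraint, so it is the solution. The formula gives:
- p = 0.010 and r = ±0.002/(0.010 × 0.990) = ±0.2020
- E[θr] = ½ × 1 × (−0.2020) = −0.1010, and E[r²] = 0.0408
- coefficient = −0.1010/0.0408 = −2.475
- f(0) = 0 + 2.475 × 0.2020 = 0.5, and f(1) = 1 − 2.475 × 0.2020 = 0.5.

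f is constant and its R² is zero.

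**3. Size under assumed models.** The documents give no effect sizes for this step. The event rate follows the simulation defaults in Section 24.3.1: placebo risk 0.10 and vaccine efficacy 0.90 give about 0.10 × (1 − 0.90) = 0.01. Two models were used.
- Log-linear: S = θ(L) + normal error, risk proportional to exp(bS + cL2), risk ratio per SD of S of 0.8, 0.6 or 0.4, and c = 0.5 or 1.0 where L2 acts on Y.
- Logistic, by quadrature: vaccine-arm risk 0.5% to 2% in the first setting below and 1% in the others.

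*L acts on Y only through S (θ is valid).*

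| Model | R² of θ | R² of the formula's f |
|---|---|---|
| log-linear | 0.30 | 0.002–0.036 |
| log-linear | 0.50 | 0.006–0.098 |
| logistic | 0.25 | 0.003–0.039 |

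*A covariate predicts Y but not S (θ is valid, with no dependence given S).* In the log-linear model, W has a log odds ratio of about 0.17–0.64 per SD given S. In the logistic model (R² of θ 0.35; log odds ratio for the covariate 0.3, 0.7, 1.0), the case/non-case difference given S is 0.24, 0.36 and 0.38 SD, with R² of 0.15, 0.28 and 0.32. The last two pass the 0.25 requirement.

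*A covariate predicts both S and Y (θ is not valid).* In the logistic model the difference given S, for θ and then for the formula, is 0.14 to 0.24 (larger), 0.32 to 0.24 (smaller) and −0.32 to +0.33 (reversed).

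**4. A projection that conditions on S.** Let g(S) = E[Y | A=1, S] and r_c(L) = E[Y | A=1, L] − E[g(S) | A=1, L]. Then

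E[f r_c] = E[f(L){Y − g(S)}] = E[Cov(f, Y | S)].

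Projecting θ off r_c sets this average conditional covariance to zero. If θ already satisfies the stated constraint, E[θ r_c] = 0 and the result is θ. In the log-linear settings this left log odds ratios within about 0.07 of zero throughout. These are large-sample results.

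**The case against.** Four points can be made for the plan.

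- **The SAP speaks of approximately solving the problem.** It does, in the rationale. But the formula itself is introduced without qualification, no weaker constraint is stated, and in step 2 above the formula moves away from the true solution.
- **The projection often helps where it is most needed.** This stands. L includes age, BMI and all other available covariates, some of which may predict both S and Y. In a log-linear grid with such a covariate, the formula left less dependence given S than θ in 41 of 48 settings, and some predictors passed the R² requirement with dependence near zero. A reader might infer that the formula always either destroys the signal or induces dependence. The calculations do not support that. A reader might also infer that θ should be used at every event count. That fails too, because θ carries log odds ratios of about 0.25–0.42 in such settings.
- **The scope is narrow.** This also stands. The binary-marker method in Section 14 needs no BIP, univariate BIPs are considered as well, and a collapsed R² stops the analysis without biasing it. Section 6 starts correlates analyses from about 150 endpoints in total. With 1:1 allocation (the default in Section 24.2.1), more than 100 in the vaccine arm would leave fewer than 50 in placebo. The branch is therefore reached mainly after longer blinded follow-up or with a weak vaccine.
- **f is refitted in each bootstrap sample.** That captures variability around the formula's own target. It does not change the target.

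**Conclusion.** The concern holds, limited to the learned multivariate BIP with more than 100 vaccine-arm events. That the formula does not solve the stated problem is algebra and rests on no assumed rate. It enforces equal marginal means of f in vaccine-arm cases and non-cases.

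The sizes rest on the assumed risk models: R² of 0.30–0.50 reduced to 0.10 or less when L acts only through S, and an induced log odds ratio of about 0.17–0.64 per SD when a covariate predicts Y but not S. Where a covariate predicts both, the formula may reduce, reverse or increase the dependence, and it does not reliably remove it.

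A reader might go on to infer that VE(s) would be biased by a comparable amount. That is not shown: only the association of W with Y given S was calculated, not its effect on the curve.

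**What to change.** Keep the projection and condition it on S.

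1. Keep Step 1 (θ) and Step 2 (m).
2. Add an estimate of g(S) = E[Y | A=1, S] and of its regression on L, both fitted with the sampling weights in the phase-two vaccine-arm data.
3. Replace r by r_c(L) = E[Y | A=1, L] − E[g(S) | A=1, L].
4. Set f = θ − {E[θ r_c]/E[r_c²]} r_c, with f = θ when r_c is zero. Say in advance how small an estimated r_c counts as zero, because the projection does not depend on the scale of r_c and would otherwise follow noise.
5. State that this sets E[Cov(f, Y | S)] to zero, which is a mean relaxation of full conditional independence, and remove the claim that the present formula solves the stated problem.
6. Report the association of W with Y given S in the vaccine arm as a diagnostic, and refit the added regressions within each bootstrap sample.

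Do not simply delete Steps 2 to 4 and use θ at all event counts: θ breaks the assumption when a covariate predicts both S and Y.

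The cost is SAP wording and one or two extra nuisance regressions. No new data are needed.

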#### **15** Correlates of Protection: Interventional Effects

In these analyses, we seek to understand whether, how, and to what extent Day 57 antibody markers impact vaccine efficacy in causal ways. We describe three approaches to this problem. Each involves consideration of a binary counterfactual outcome Y(a, s) (e.g., indicator of the COVID disease endpoint by a pre-specified time) under a hypothetical intervention that both sets randomization assignment A = a and sets the Day 57 immunologic marker S to a fixed value or based upon a random draw from a analystspecified distribution. Below, we assume that S is scalar-valued, but some of the approaches below naturally extend to the case where a vector of immunologic markers are considered (currently such analyses are not planned). Given the central goal to develop a parsimonious surrogate endpoint based on a single immunoassay, the main analysis will use each of the methods to assess each of the five quantitative readouts (not baseline-subtracted) separately as CoPs, adjusting for the same set of baseline covariates as used in the CoR analyses previously described in Section 12.

#### 15.1 CoP: Controlled Vaccine Efficacy

We first describe the controlled vaccine efficacy curve defined as

$$CVE(s) = 1 - \frac{P(Y(1,s) = 1)}{P(Y(0) = 1)}$$

The value CVE(s) takes represents the relative decrease in endpoint frequency achieved by administering vaccine and setting Day 57 immunologic marker level to s compared to the placebo control intervention. Under our approach, the value of CVE(s) is assumed to be monotone non-decreasing in s; in other words, vaccine efficacy can only potentially be improved by setting greater marker levels. The extent to which the marker plays a role in determining vaccine efficacy can be determined by the degree of flatness of the graph of CVE(s) versus s.

In addition, because the primary study cohort for correlates analysis is naive to SARS-CoV-2, each of the Day 57 markers S has no variability in the placebo arm [all values are 'negative,' below the assay lower limit of detection (LLOD)]. Therefore, advantageously in this setting CVE(s) has a special connection to the mediation literature, where CVE(s = LLOD) is the natural direct effect, and vaccine efficacy is 100% mediated through S if and only if CVE(s = LLOD) = 0. Thus inference on CVE(s = LLOD) evaluates full mediation.

Since P(Y(0) = 1) = P(Y = 1 | A = 0) in view of vaccine versus placebo randomization, the controlled vaccine efficacy CVE(s) at level s can be identified using the fact that

$$P(Y(1,s) = 1) = E[P(Y = 1 | S = s, A = 1, X)]$$

whenever Y(1,s) and S are independent given A = 1 and a vector X of covariates, and P(S = s | A = 1, X) > 0 almost surely. In other words, identification of the controlled vaccine efficacy requires that a rich enough

set of covariates be available so that deconfounding of the relationship between endpoint Y and marker S is possible in the subpopulation of vaccine recipients, and that marker level S = s may occur within each subpopulation defined by values of the covariates X (positivity).

For each s, the identified parameter corresponding to CVE(s) is an irregular parameter within nonparametric models, making its estimation at root-n rate impossible; this significantly complicates estimation and inference on CVE(s). Fortunately, the monotonicity of  $s \mapsto \text{CVE}(s)$  provides an opportunity to circumvent these difficulties. Similarly to Westling et al. (2020a)'s approach for the causal dose-response function, we will use the general methodological template proposed in Westling and Carone (2020) to derive (i) a nonparametric Grenander-type estimator of CVE(s) and (ii) a plug-in confidence interval for CVE(s) based on an asymptotic Chernoff limit. This estimator will require, as an intermediate step, estimation of several nuisance functions, including the outcome regression P(Y = 1 | S = s, A = 1, X = x) and the propensity score P(S = s | X = x, A = 1). These nuisance functions will be estimated using the Superlearner ensembling algorithm with a rich library including both parametric regression methods as well as flexible machine learning tools.

The monotonicity-based procedure we will develop facilitates statistical inference for CVE(s) for each s separately, where point estimates and 95% confidence intervals for CVE(s) will be presented. However, it is also of interest to investigate whether the Day 57 marker plays a role in determining vaccine efficacy. To do so, we will formally test the null hypothesis

$$H_0$$
: CVE $(s)$  is constant in  $s$ 

against various alternatives. We will first adapt the approach of Westling (2020) to devise a nonparametric omnibus test of this null hypothesis. We will also construct a nonparametric directional test of this hypothesis tailored to alternatives under which CVE(s) is monotone in s, along the lines of Hall and Heckman (2000), for example. Leveraging the known monotonicity of the controlled vaccine efficacy will provide greater power than omnibus tests.

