#### 6 Timeline/Sequencing of Correlates Analyses

The correlates analyses are initiated by the availability of (a) a data set defined at or after the primary analysis data set triggered by the accrual of a certain number of primary endpoints (typically approximately 150 in U.S. phase 3 studies); and (b) Day 1, 57 antibody marker data from correlateseligible COVID primary endpoint cases from at least 25 baseline negative vaccine recipients. The latter requirement ensures that there are enough endpoint cases to achieve worthwhile precision for CoR analyses. The HVTN 505 trial serves as a precedent where 25 evaluable vaccine recipient cases provided enough data to reasonably characterize correlates of risk for a preventive candidate HIV vaccine (Janes et al., 2017; Fong et al., 2018; Neidich et al., 2019; Gilbert et al., 2020b). In addition, simulation studies show that correlates analyses at 20 endpoints have notably lower precision.

Table 4 shows the minimum number of baseline negative vaccine recipient endpoints evaluable for correlates analyses that are required before conducting the various planned correlates analyses.

Correlates Analysis Type	Number
CoRs (Risk Prediction Modeling)	
a. (Semi)parametric models with strongly parametrized associations:	
Cox, hinge/threshold logistic regression	25
b. Flexible parametric models: Generalized additive model	35
c. Nonparametric thresholds: Donovan et al. $(2019)/$	
van der Laan et al. (2020)	35
d. Superlearner estimated optimal surrogate	35
CoP: Correlates of VE	50
CoP: Controlled VE	50
CoP: Stochastic Interventional VE	50
CoP: Mediators of VE	50

Table 4: Minimum Numbers of Evaluable Endpoints in Baseline Negative Vaccine Recipients toInitiate Correlates Analyses

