If certain strata do not have enough eligible participants available for sampling, then additional sampling is done from other strata to keep the total immunogenicity subcohort sample size to close to 1620. A separate USG COVID-19 Response Team Antibody Marker sampling plan describes the algorithm, available upon request.

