Only this Superlearner analysis uses data from multiple assays and multiple readouts as input features; the other analyses consider one Day 57 biomarker at a time. The positivity

assumptions are as follows. Controlled VE: P(S = s | A = 1, X) > 0 almost surely. Stochastic Interventional VE:  $s_i \in S \implies s_i + \delta \in S | A = 1, X = x$  for all  $x \in \mathcal{X}$  and i = 1, ..., n. Mediators of VE: P(S = s | A = 1, X) > 0 almost surely and

P(S = s | A = 0, X = x) > implies P(S = s | A = 1, X = x) > 0. The quantitative analysis will require that the largest value S observed in the placebo is larger than the smallest value of S observed in the vaccine recipients. This assumption would naturally be satisified for the tertiles analysis. For quantitative S, the assumption is weaker for the Stochastic Interventional VE analysis, such that it is possible that only this analysis of the three will be done.
Some of the analyses include parametric assumptions for characterizing associations (Cox model and threshold analyses, Cox model versions of Controlled VE analyses) and others are nonparametric or approximately so (all other analyses). If parametric and nonparametric analyses of the same type (e.g., Cox model vs. nonparametric CoR analysis of the same association parameter; Controlled VE Cox model vs. nonparametric monotone dose-response) suggest contradictory results, then the interpretation from the nonparametric analysis will be prioritized, given it is more robust and less likely to be an incorrect result. The diagnostic testing of the parametric assumptions will aid this interpretation. As noted above, if the nonparametric analysis suggesting a contradictory result requires a positivity assumption, then its results will only be prioritized if diagnostics support feasibility of the positivity assumption.

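### Section 15.1 plans Chernoff-limit intervals for controlled VE at every marker level, including the range ends, the LLOD and flat curves, where that limit does not hold

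*Combined protocol and SAP*

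**What the plan says.** - **Estimator and interval.** SAP Section 15.1 specifies a Grenander-type estimator of CVE(s) and "a plug-in confidence interval for CVE(s) based on an asymptotic Chernoff limit". Inference is pointwise, and "point estimates and 95% confidence intervals for CVE(s) will be presented". The section gives no range of s, no slope estimator for the plug-in, and no other interval for the ends, for point masses or for zero slope.
- **How the curve is read.** The marker's role "can be determined by the degree of flatness of the graph of CVE(s) versus s". At the bottom of the range, the level below which placebo recipients are expected to lie is itself a target: "Thus inference on CVE(s = LLOD) evaluates full mediation".
- **Point masses.** Section 2.1 sets values below the LLOD to LLOD/2 and, for correlates analyses, caps values at the ULOQ.
- **Weight of the result.** Under Section 16, if parametric and nonparametric analyses of the same type conflict, "then the interpretation from the nonparametric analysis will be prioritized". Where the nonparametric analysis needs positivity, this applies only if diagnostics support it.
- **Safeguards present.** Section 15.1 also plans an omnibus test and a directional test of constant CVE(s). Section 12.3.3 limits the Cox plot for S at or above s to thresholds with 5 or more cases. Section 15.1 has no matching limit.

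**The concern.** The Chernoff limit for a monotone estimator holds at an interior point of a continuous marker distribution where the curve has a non-zero slope. The plan uses it where each of these conditions can fail. The level s = LLOD is either the edge of the support or a point mass at LLOD/2. The top is either the edge or a point mass at the ULOQ. A flat curve is the null case of interest, and there the scale of the limit is zero.

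At stake is how a published curve and its intervals are read. With a continuous marker that has nothing to do with risk, the ends of the curve bend towards no protection at the bottom and complete protection at the top, and the nominal 95% intervals are far too narrow.

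**Working it through.** The SAP gives no bias or coverage figure for this estimator, so there is none to reproduce.

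**Inputs from the SAP**
- Minimum vaccine cases, Table 4: "CoP: Controlled VE 50".
- Sampled non-cases: 6 × 150 = 900 (Table 5, vaccine, baseline negative). The table total is 6 × (150 + 20 + 50 + 50) = 1,620, in line with the aim to "keep the total immunogenicity subcohort sample size to close to 1620".
- True VE 0.90, the simulation default in Section 24.3.1; 0.70 was also run.

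**Assumptions not in the SAP**
- Vaccine-arm N of 13,500 or 14,000 (a run with 5,000 gives the same pattern).
- No covariates, and placebo risk known.
- Slope taken from the fitted curve over a half-window of 0.1 to 0.4 on the marker percentile scale.

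The fit is weighted isotonic regression, with cases weighted 1 and non-cases weighted by the inverse sampling fraction. There were 1,000 to 2,000 trials per setting. The marker is unrelated to risk unless stated.

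**1. Highest value, continuous marker.** The fitted risk is zero, so CVE is 100%, unless the top sampled participant is a case. The chance of 100% is 900/(900 + cases):
- 50 cases: 900/950 = 94.7%; simulated 94-96%.
- 400 cases: 900/1,300 = 69.2%; simulated 69%.

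The stretch drawn at 100% lies above the highest case. Its median share of the marker distribution is 1 − 0.5^(1/50) = 1.4%; simulated 1.2-1.3%.

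**2. Lowest value, continuous marker.** The limit law is P(fitted risk / true risk > x) = 1/x.
- CVE ≤ 0.80 means x = 0.20/0.10 = 2, so 50%; simulated 51-53%.
- CVE ≤ 0 means x = 1.00/0.10 = 10, so 10%; simulated 11-12%.
- The median is at x = 2, CVE 0.80; simulated 0.78-0.79, and still 0.78 with 400 cases.
- At VE 0.70 the median is 1 − 2 × 0.30 = 0.40; simulated 0.37-0.40.

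The share of the marker distribution with estimated CVE of 0.80 or less averages 0.9%.

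**3. Interior.** Medians are 0.88 at the 10th percentile, 0.90 at the 50th and 0.92 at the 90th. The median spurious rise is 0.21 from lowest to highest value, and 0.04 from the 10th to the 90th percentile.

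**4. Point masses.** With a share p at the ULOQ, 100% at the top needs no case there: (1 − p)^50.
- p = 2%: 36%; simulated 36%.
- p = 5%: 7.7%; simulated 8%.
- p = 10%: 0.5%; simulated 0.5%.

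With 2% of vaccinees at the LLOD the median CVE there is 0.83-0.84, and 0 or less occurred in none of 1,500 trials. With 10% the median is 0.87, and 0.50 or less never occurred.

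**5. Intervals.** On the CVE scale the half-width is 0.998 × (4dκ/N)^(1/3) / r0. Here d is the slope of risk on the percentile scale, r0 the placebo risk, and κ = r(1 − r)² + r²(1 − r)/π with π = 900/(N − cases).

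With 50 cases and N = 13,500: r = 50/13,500 = 0.0037, r0 = 0.0037/0.10 = 0.037 and κ = 0.0039. A flat curve has d = 0, so the half-width is 0. For comparison, if risk falls as exp(−2.5q) over percentile q, then at the median d = 0.0072 and κ = 0.0030, and the half-width is 0.050.

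Simulated coverage of nominal 95% plug-in intervals, continuous marker, over the slope windows tried:

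| Curve, cases | Lowest value | 10th-90th percentile | Highest value |
|---|---|---|---|
| Flat, 50 | 0.19-0.26 | 0.28-0.87 | 0.01 |
| Flat, 400 | 0.11-0.13 | 0.29-0.92 | 0.05-0.06 |
| Sloped, 50 | 0.32-0.34 | 0.62-0.96 | 0.00-0.01 |
| Sloped, 400 | 0.19 | 0.89-0.99 | 0.05-0.06 |

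The last row shows that the interval works where its theory applies. With flat risk and point masses of 2% or 10% at each end, coverage at the ends is 0.00-0.38.

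**The case against.** **Full mediation.** A reader might infer that an irrelevant marker would be reported as fully mediating VE. The documents do not support this. CVE(s = LLOD) is identified only if vaccinees occur at that level: Section 15.1 requires positivity, Table 10 makes the analysis conditional on it, and Section 15.3 wants at least 10% of vaccinees at the placebo value for the mediation analysis. Where that holds there is a point mass, and the point estimate stays well away from zero. This objection stands. What remains is the interval at the point mass.

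**Spikes by construction.** A reader might also infer that the curve always spikes at both ends. It does so for a continuous marker, over a small share of participants. A few percent of values at the ULOQ largely removes the top spike, and the SAP does not state that share.

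**Tests and other analyses.** Section 15.1 tests constancy formally, which protects the yes/no decision. The Section 16 rule covers only conflicts of the same type, subject to positivity. Controlled VE is one of four correlate-of-protection approaches, and Cox and tertile versions exist. All this stands and lowers the priority. None of it corrects the plotted curve or its intervals.

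**Not the planned procedure.** The simulation omits covariates and the Superlearner nuisance fits, and the SAP does not name a slope estimator. Exact coverage would therefore differ. The results at the two ends do not depend on the slope choice, and every window tried under-covered for a flat curve.

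**Conclusion.** The point holds in a limited form. The interval method in Section 15.1 is not valid at the ends of the marker range, at point masses or for a flat curve, and the plan sets no limit that keeps it away from them.

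For a continuous, irrelevant marker at the plan's minimum of 50 cases, the estimate at the lowest value has median about 0.79 against a true 0.90, and the highest value is drawn at 100% in about 95% of trials. More cases do not cure the bottom and only partly reduce the top. The distortion of the estimate affects roughly the outer 1-2% of the marker distribution. With point masses the estimate is mostly sound, but the interval is not. Under a flat curve the intervals are too narrow in the interior as well.

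These sizes rest on the assumed vaccine-arm N, no covariates and known placebo risk. The change is recommended; it is not a condition for running the analysis.

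**What to change.** 1. **Point masses.** At LLOD/2 and at the ULOQ cap, treat the marker as a discrete level. Estimate P(Y(1,s) = 1) there by TMLE or a one-step estimator, with a Wald-type or small-sample interval. Use this for the full-mediation assessment, and state that s = LLOD there means the LLOD/2 level. If no vaccinees are at that level, make no inference on CVE(LLOD).
2. **Range.** Show the monotone curve and its intervals only in the interior, for example from the 10th to the 90th percentile and with at least 5 vaccine cases on each side of s, in line with the 5-case rule in Section 12.3.3. The case rule matters: in the sloped example with 50 cases only about 50 × 0.025 = 1.3 cases are expected above the 90th percentile, so the display would stop lower. Apply the Section 16 priority rule only inside this range, and name the slope estimator.
3. **Flat curves.** Trimming does not repair the intervals here. State that the Chernoff intervals are not valid when the curve is flat, and that whether the marker matters is judged from the planned tests of constant CVE, not from the graph or its intervals. If constancy is not rejected, report the tertile controlled-VE estimates, already listed in Table 10, with Wald intervals alongside. In the flat simulations, log-scale Wald intervals by tertile covered 95-96%.

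**Cost.** SAP wording, an added discrete-level estimator for at most two levels per marker, and a curve shown over a shorter range. No new data are needed.
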